11.3.6 Laboratory Assessments

Safety laboratory tests, including hematology, biochemistry, and bone markers will be performed as specified below, and in the Schedule of Assessments ([Table 1](#)). Blood samples should be obtained prior to trial drug dosing. In total approximately 280 mL blood is drawn.

Safety laboratory tests are to be performed and reviewed by the Investigator or qualified designee (e.g., physician's assistant, nurse practitioner). Safety laboratory samples will be analyzed via central laboratories.

11.3.6.1 Hematology

Hemoglobin, hematocrit, red blood cell (RBC) count, white blood cell (WBC) count with differential, and platelet count will be measured at Screening, at the Optimization and Stabilization Phase visits, and at every trial visit (with the exception of Visit 2-phone assessment).

11.3.6.2 Biochemistry

The following parameters will be measured (or calculated) at every trial visit (with the exception of Visit 2-phone assessment): Sodium, potassium, chloride, bicarbonate, blood urea nitrogen, creatinine, CLcr (estimated), glucose, calcium, phosphorous, alkaline phosphatase, ALT, AST, international normalized ratio (INR), gamma-glutamyl transferase (GGT), lactic dehydrogenase, conjugated bilirubin, total bilirubin, total protein, albumin, amylase, uric acid, and C-reactive protein.

In case of suspected liver injury based on increased ALT, AST, alkaline phosphatase, or total bilirubin, the tests should be repeated at 48-72 hours for evaluation of the event course/confirmation. When drug-induced liver injury (DILI) is suspected based on the transferases values, the liver functionality needs to be evaluated by the bilirubin and INR for confirmation/information of DILI.

Cholesterol and triglycerides will be measured orally fasting at Visits 1 (Day 1) and 10 (Day 169/Week 24).

Magnesium and zinc will be measured at Visits 1 (Day 1), 7 (Day 85/Week 12), and 10 (Day 169/Week 24) only.

11.3.6.3 Bone Markers

The standard bone markers collected are: 25OH vitamin D, parathyroid hormone (PTH), thyroid stimulating hormone (TSH; thyrotropin), P-CTx (collagen I, C-terminal telopeptide-fragments), a marker of bone resorption and P-PINP (Pro-collagen, N-terminal pro-peptide) a marker of bone

formation. Blood samples for bone markers will be obtained at Visit 1 (Day 1) and Visit 10 (Day 169/Week 24) only.

11.3.6.4 Urinalysis

Urinalysis will be measured at every trial visit (with the exception of Visit 2-phone assessment). Urinalysis will include: blood, glucose, leukocytes, pH, osmolality, protein, sodium and potassium.

11.3.6.5 Pregnancy Screen

A pregnancy test (serum beta-human chorionic gonadotropin [hCG]) will be completed for all females of childbearing potential at Screening, at Optimization Phase visit 1 (Op1), Stabilization Phase visit 1 (St1), at Visit 1 (Day 1), and from Visit 5 (Day 29/Week 4) to Visit 10 (Day 169/Week 24). Sterilized or infertile patients, i.e., patients who have undergone surgical sterilization (vasectomy/bilateral tubectomy, hysterectomy, and bilateral ovariectomy) or women who are postmenopausal, which is defined as > 52 years of age and 12 months or more with no menstruation prior to enrollment and/or as FSH level >30 mIU/mL (as measured at site) are not regarded as being of childbearing potential.

11.3.6.6 Immunogenicity

Serum samples will be obtained prior to dosing (if dosing occurs on the visit day) at Visit 1 (Day 1), 4 (Day 15/Week 2), 5 (Day 29/Week 4), 6 (Day 57/Week 8), 7 (Day 85/Week 12), 10 (Day 169/Week 24), and Follow-up Visit (Day 197/Week 28) (if applicable) to determine the presence of ADA and the ADA titer. Each ADA sample will contain 5 mL of blood, resulting in 30 mL (35 mL with Follow-up Visit) of blood drawn for ADA analysis.

The serum samples will be analyzed using a tiered approach (screening, confirmation, and titration of confirmed anti-glepaglutide-antibody positive samples), followed by characterization of ADA-positive samples for *in vitro* ZP1848-neutralizing potential and cross-reactivity to the major metabolite (ZP1848₁₋₃₄) and GLP-2. Results will not be revealed to the sites.

All ADA samples will be retained at the special lab (Syrinx Bioanalytics Oy, Finland) or long-term storage facility (MLM Medical Labs GmbH, Germany) until drug approval by the US FDA and/or EMA or 15 years after end of trial at maximum. The retained ADA samples may be used for further confirmation and characterization of detected ADAs if required by health authorities or for safety reasons.

11.3.6.7 Pharmacokinetics

A blood sample will be obtained prior to administration of trial drug (if dosing occurs on the visit day) at every trial visit during the Treatment Phase (except for Visit 2-phone assessment) and the Follow-up Visit (Day 197/Week 28). The PK sampling schedule is set in order to be able to correlate PK values to ADA data and to obtain sufficient information from the dosing regimens tested. Results will not be revealed to the sites.

Each PK sample will contain 6 mL of blood, resulting in 60 mL of blood drawn for PK analysis.

11.3.6.8 HIV, Hepatitis B, and Hepatitis C

A blood sample will be obtained at screening to confirm the HIV, hepatitis B and C status. If positivity is confirmed, the patient will be excluded from participation in the trial.

11.4 Adverse and Serious Adverse Events

Timely, accurate, and complete reporting and analysis of safety information from clinical trials are crucial for the protection of patients. Investigators and the Sponsor are mandated by regulatory agencies worldwide to report the safety information.

11.4.1 Definitions

11.4.1.1 Adverse Events

An AE is any untoward medical occurrence in a clinical trial patient administered a medicinal (investigational or non-investigational) product and which does not necessarily have a causal relationship with this treatment. An AE can therefore be any unfavorable and unintended sign (including an abnormal laboratory finding), symptom, or disease temporarily associated with the use of a product, whether or not related to the product.

AEs include:

- A clinically significant worsening of a concomitant illness
- A clinical laboratory AE: a clinical abnormality which is clinically significant, i.e., any abnormality that suggests a disease and/or organ toxicity and is of a severity that requires active management. Active management includes active treatment or further investigations, e.g., change of dose or more frequent follow-up due to the abnormality.

The following should **not** be considered as AEs:

- Pre-existing conditions, including those found as a result of screening procedures (pre-existing conditions should be reported as medical history or concomitant illness).
- Pre-planned procedure, unless the condition for which the procedure was planned has worsened from the first trial-related activity after the patient has signed the informed consent.

When assessing an AE, the following definitions will be used:

Severity:

- **Mild:** No or transient symptoms, no interference with the patient's daily activities
- **Moderate:** Marked symptoms, moderate interference with the patient's daily activities
- **Severe:** Considerable interference with the patient's daily activities, which the patient finds unacceptable. A severe reaction does not necessarily deem the AE as serious and an SAE are not always severe in nature.

Causality:

- **Probably:** Good reason and sufficient documentation to assume a causal relationship
- **Possibly:** A causal relationship is conceivable and cannot be dismissed
- **Unlikely:** The event is most likely related to etiology other than the product
- **Not related:** No relationship to product.

Outcome:

- **Recovered/resolved:** The patient has fully recovered, or by medical or surgical treatment, the condition has returned to the level observed at the first trial-related activity after the patient signed the informed consent
- **Recovering/resolving:** The condition is improving and the patient is expected to recover from the event. This term is only applicable if the patient has completed the trial or has died from another AE
- **Recovered/resolved with sequelae:** The patient has recovered from the condition, but with lasting effect due to a disease, injury, treatment, or procedure. If a sequela meets an SAE criterion, the AE must be reported as an SAE
- **Not recovered/not resolved:** The condition of the patient has not improved and the symptoms are unchanged, or the outcome is not known
- **Fatal:** This term is only applicable if the patient died from a condition related to the reported AE. Outcomes of other reported AEs in a patient before he/she died should be assessed as “recovered/resolved”, “recovering/resolving”, “recovered/resolved with sequelae”, or “not recovered/not resolved”. An AE with fatal outcome must be reported as an SAE
- **Unknown:** This term is only applicable if the patient is lost to follow-up.
-

11.4.1.2 Adverse Events of Special Interest (AESI)

In this trial the following events are to be regarded as AESI, should they occur: neoplasms (malignant and benign), suspicion of liver injury, pancreatitis, and cholecystitis.

If the event is reported as an SAE, the timelines for SAE reporting apply. If the event is reported as non-serious AE, it should be reported in the dedicated eCRF page within 2 working days (if at all possible) of Investigator's first knowledge.

The event-specific information that needs to be captured in addition to the standard AE information is presented below:

Neoplasms:

Information on histopathology (date of examination and results), imaging (if imaging is performed), TNM staging, history of cancer (the patient's and family), treatment received for this event, and an event narrative. Copies of images (if performed) should be stored at each site. A retrospective imaging review may be performed if deemed necessary.

Suspicion of liver injury:

Suspicion of liver injury* is defined as:

- ALT or AST increasing more than 3 times from baseline value, or
- ALT or AST $> 5 \times$ ULN and total bilirubin $> 2 \times$ ULN, or
- ALT or AST $> 5 \times$ ULN and INR > 1.5

* In that case, the tests should be repeated at 48-72 hours for evaluation of the event course/confirmation. Furthermore, additional information needs to be provided by the site,

e.g. physical examination, information on alcohol consumption, concomitant therapy (including herbals).

- Narrative of the event should include:
 - Clinical signs and symptoms and how they developed over time. Aspects like e.g. abdominal pain, nausea, vomiting, jaundice, fever, rash, abdominal tenderness, hepatomegaly, splenomegaly, blood pressure, peripheral edema, jugular venous distension, signs of ascites, recent weight gain should be considered and described.
 - Information on relevant medical history, alcohol consumption, and relevant concomitant therapy (including herbals).
 - Lab tests (at local lab, if needed): as a minimum ALT, AST, Bilirubin (direct and total) and INR. Other tests may be warranted as clinically indicated.
 - Imaging diagnostic (ultrasound/CT scan/MRI/Other imaging modality). Copies of images (if performed) should be stored at each site.
 - Biopsy results (if performed).

Pancreatitis:

- Narrative of the event should include
 - Clinical signs and symptoms and how they developed over time. Aspects like pain (character of the pain including the anatomical region (e.g. sudden and in center abdomen) +/- irradiating pain in the back), tenderness of the abdomen, diarrhea, indigestion, fever, jaundice) should be considered and described.
 - Information on relevant medical history, alcohol consumption, and relevant concomitant therapy (including herbals).
 - Lab tests (at local lab, if needed): pancreatic and liver function tests, including lipase, amylase, ALT, AST, bilirubin, and alkaline phosphatase. Other tests may be warranted as clinically indicated.
 - Imaging diagnostic (ultrasound/CT scan/MRI/Other imaging modality). Copies of images (if performed) should be stored at each site.
 - Biopsy results (if performed).

Cholecystitis:

- Narrative of the event should include
 - Clinical signs and symptoms and how they developed over time. Aspects like pain (character of the pain including the anatomical region (e.g. sudden, after a large meal, in upper right or center abdomen) +/- irradiating pain to right shoulder or back), tenderness of the abdomen, nausea, vomiting, and fever should be considered and described.
 - Information on relevant medical history, alcohol consumption, and relevant concomitant therapy (including herbals).

- Lab tests (at local lab, if needed): liver function tests, including ALT, AST, bilirubin, and alkaline phosphatase. Other tests may be warranted as clinically indicated.
- Imaging diagnostic (ultrasound/X-Ray/CT scan/MRI/Other imaging modality). Details like presence of gall bladder stones and common bile duct diameter should be reported, if available.

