7.3 Exclusion Criteria

The patient must be excluded from the trial if he or she meets any of the following criteria:

1. More than 2 SBS-related or PS-related hospitalizations (e.g., catheter related bacteremia/sepsis, bowel obstruction, severe water-electrolytes disturbances, etc.) within 6 months prior to Screening.
2. Poorly controlled inflammatory bowel disease (IBD) that is moderately or severely active or fistula interfering with measurements or examinations required in the trial.
3. Bowel obstruction.
4. Known radiation enteritis or significant villous atrophy, e.g., due to active celiac disease.
5. Cardiac disease defined as: decompensated heart failure (New York Heart Association [NYHA] Class III-IV), unstable angina pectoris, and/or myocardial infarction within the last 6 months prior to Screening.
6. Clinically significant abnormal ECG as judged by the Investigator.
7. Repeated (2 or more consecutive measurements separated by at least 15 minutes) systolic blood pressure measurements > 180 mm Hg.
8. HIV (human immunodeficiency virus) positive, acute liver disease, or unstable chronic liver disease.
9. Any history of colon cancer. History of any other cancers (except margin-free resected cutaneous basal or squamous cell carcinoma or adequately treated *in situ* cervical cancer) unless disease-free state for at least 5 years.
10. Estimated creatinine clearance (CLcr; by the Cockcroft-Gault formula) < 30 mL/min.
11. Hepatic impairment defined as:
 - a. Total bilirubin $\geq 2 \times$ the upper limit of normal (ULN), or
 - b. Aspartate aminotransferase (AST) $\geq 5 \times$ ULN, or
 - c. Alanine aminotransferase (ALT) $\geq 5 \times$ ULN
12. Use of GLP-1, GLP-2, human growth hormone (HGH), somatostatin, or analogs thereof, within 3 months prior to Screening.
13. Use of dipeptidyl peptidase (DPP)-4 inhibitors within 3 months prior to Screening.
14. Systemic immunosuppressive therapy that has been introduced or has been unstable within 3 months prior to Screening.
15. Unstable biological therapy (e.g. anti-TNF- α , natalizumab, etc.) within 6 months prior to Screening, including significant changes in doses or switch of drug.

16. Females of childbearing potential, who are pregnant, breast-feeding, intend to become pregnant or are not using highly effective contraceptive methods. Highly effective contraception methods and definition of child-bearing potential are described in [Section 11.4.4](#).

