7.5 Patient Withdrawal or Discontinuation from Trial Treatment

The patient is free to withdraw consent at any time during the trial. The patient's request to withdraw from the trial must always be respected.

All data collected from a withdrawn patient prior to withdrawal and during the final visit will be included in the analyses of the trial data. Although a patient is not obliged to give his/her reason(s) for withdrawing consent, the Investigator must make a reasonable effort to ascertain the reason(s), while fully respecting the patient's rights. An end of trial form must be completed and final drug accountability done even when patients are not able to come for a trial visit.

Only patients who withdraw their consent will be considered as withdrawn from the trial.

For patients who permanently discontinue from trial treatment (i.e. there is no plan to resume trial treatment or to enter the Extension Trial) every effort must be made to ensure patients attend and complete all scheduled visit procedures to the extent possible. Patients should stay in the trial regardless of compliance with trial drug, assessments, or visit schedule.

The investigators should make a special effort to ensure that all patients complete the assessment of actual PS volume in Week 24 (primary endpoint).

Patients who permanently discontinue from trial treatment and the trial (without withdrawal of consent) should be asked to come to the site for an EOT visit during which all general, safety, and laboratory assessments should be performed as detailed in the schedule of assessments. During this visit, the Investigator should also discuss further treatment options for SBS with the patient. Note: if a patient is discontinued during a trial visit, efforts should be made to complete all trial-related assessments for the EOT Visit. If not participating in the Extension Trial, the patient should attend the FU/Final visit.

A patient must be discontinued from trial treatment if:

1. Any safety concerns or AEs that in the opinion of the Investigator might place the patient at unacceptable risk, including any deterioration of a patient's health state, especially in terms of the frequency and volume of total PS.
2. Any malignancy.
3. Increased liver values, defined as:
 - a. ALT or AST >3 times baseline value lasting more than 2 weeks*, or
 - b. ALT or AST >5 × ULN and total bilirubin >2 x ULN*, or
 - c. ALT or AST >5 × ULN and INR >1.5*, or

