 - d. ALT or AST >5 × ULN with the appearance of fatigue, nausea, vomiting, right upper quadrant pain or tenderness, fever, rash, and/or eosinophilia (>5%) %)*.
4. Pregnancy or intention to become pregnant.
5. The patient requires treatment with prohibited medications (see [Section 8.6](#)).

Patients can be discontinued from trial treatment if:

1. A patient was randomized despite it was later identified as having violated any of the inclusion, exclusion, or randomization criteria. The Investigator must discuss with the Sponsor's Medical Monitor if it is safe for the patient continue the trial treatment.

If a patient prematurely discontinues trial treatment, the primary reason must be specified in the eCRF and the Investigator must undertake procedures similar to those for the relevant visits as soon as possible. The intent should be to follow the patient to the extent possible according to the planned visit schedule and assessments with the purpose of following the safety and efficacy of the patients. Reason for trial visits not having been performed must be documented.

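### One liver criterion that forces treatment discontinuation, Protocol 7.5(3d), is missing from the definition of the liver-injury AESI, so the liver AESI count can miss patients who enter with raised transaminases

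*Protocol*

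**What the plan says.** **Stopping rule.** Protocol 7.5 opens its list with "A patient must be discontinued from trial treatment if". Item 3 has four liver criteria:
- 3a: "ALT or AST >3 times baseline value lasting more than 2 weeks"
- 3b: either transaminase above 5 × ULN together with total bilirubin above 2 × ULN
- 3c: either transaminase above 5 × ULN together with INR above 1.5
- 3d: "ALT or AST >5 × ULN with the appearance of fatigue, nausea, vomiting, right upper quadrant pain or tenderness, fever, rash, and/or eosinophilia"

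**AESI definition.** Protocol 11.4.1.2 names four AESIs: "neoplasms (malignant and benign), suspicion of liver injury, pancreatitis, and cholecystitis". For the liver, the words "Suspicion of liver injury* is defined as" introduce three alternatives. The first is "ALT or AST increasing more than 3 times from baseline value, or" and the other two match 3b and 3c. Symptoms are mentioned only as content for the narrative of an event that already qualifies.

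**Entry.** Exclusion 11 in Protocol 7.3, under "Hepatic impairment defined as", removes patients with ALT or AST at or above 5 × ULN. Exclusion 8 removes acute and unstable chronic liver disease.

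**Use of the label.** AESI status brings a dedicated eCRF page and a structured liver narrative (Protocol 11.4.1.2). It also decides entry to the AESI table, the AESI listing and the AESI risk differences (SAP 7.2). The SAP gives no liver definition of its own, so the protocol's applies.

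**The concern.** The two lists treat one pattern inconsistently: 3d is grave enough to end treatment on liver grounds, yet it is not a suspicion of liver injury for AESI purposes. Neither document gives a reason for leaving it out.

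For a patient with normal baseline enzymes this has no effect, because a value above 5 × ULN is also above 3 × baseline. It matters when the baseline is already raised. The population makes that plausible: Protocol 4.1 names liver damage as a complication of parenteral support, and Protocol 10.1 records any history of cholestasis, steatosis or cirrhosis.

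With about 36 patients per arm, single cases matter. SAP 7.2 also replaces the summary by a listing when there are fewer than 5 events of a type, and AESIs are one of the types named. One uncounted event could decide whether a table is produced, and the listing would omit that event too.

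**Working it through.** The documents state no figure on this point, so there is none to reproduce. The check asks whether every case meeting a 7.5(3) criterion also meets an AESI criterion.

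**Inputs.** Let *b* be the patient's baseline and *v* the on-treatment value of a transaminase, both in multiples of ULN. Exclusion 11 gives *b* < 5. The stopping criteria come from Protocol 7.5 and the AESI criteria from 11.4.1.2. I read the first AESI criterion as *v* > 3*b*. A more literal reading, a rise of more than three baselines (*v* > 4*b*), would open the gap earlier, at 5/4 = 1.25 × ULN, so the reading used here gives the smaller gap.

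**Step 1: compare the lists.**

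| Stopping criterion | AESI counterpart | Covered? |
|---|---|---|
| 3a: *v* > 3*b* for more than 2 weeks | *v* > 3*b*, no duration | Yes, as a subset |
| 3b: *v* > 5, bilirubin > 2 × ULN | the same | Yes |
| 3c: *v* > 5, INR > 1.5 | the same | Yes |
| 3d: *v* > 5, symptoms and/or eosinophilia | none | Only if another criterion is also met |

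A grid check (*b* from 0.3 to 4.9, *v* from 0.3 to 19.9, bilirubin, INR and symptoms each on either side of their limits) agreed. Criteria 3a, 3b and 3c gave no uncovered combination; only 3d did.

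**Step 2: when does 3d escape?** All of these must hold:
- *v* > 5 with a listed symptom or eosinophilia
- *v* ≤ 3*b*, and the other transaminase also no more than 3 times its own baseline
- total bilirubin ≤ 2 × ULN
- INR ≤ 1.5

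The first two require 5 < *v* ≤ 3*b*, which is possible only if *b* > 5/3 = 1.67. With *b* ≤ 1.67, every 3d case already meets the first AESI criterion.

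**Step 3: the uncovered range**, for baselines that exclusion 11 allows:

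| Baseline (× ULN) | 3 × baseline | Value that stops treatment under 3d without being an AESI (× ULN) |
|---|---|---|
| 1.5 | 4.5 | none |
| 2 | 6 | above 5, up to 6 |
| 3 | 9 | above 5, up to 9 |
| 4 | 12 | above 5, up to 12 |
| 4.9 | 14.7 | above 5, up to 14.7 |

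**Example.** Baseline 2.0 and peak 5.5 × ULN with fever and rash give 5.5/2.0 = 2.75 × baseline. If bilirubin, INR and the other transaminase stay within the limits above, 3d is met and no AESI criterion is.

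**Step 4: with the lists joined.** Since 3a to 3c are already covered, counting events that meet either list adds only the 3d cases in Step 3, and no uncovered combination remains.

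**The case against.** **The gap is narrow.** It needs a raised baseline, a value in a bounded range, the other transaminase not above 3 × its own baseline, bilirubin and INR not above their cut-offs, and symptoms or eosinophilia, in a trial that excludes acute and unstable chronic liver disease. This stands, and it is why the subset is probably small.

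**The events are seen elsewhere.** A reader might infer that these liver events drop out of safety reporting. The documents do not support that. SAP 7.2 tabulates and lists AEs leading to treatment discontinuation and applies the broad *Hepatic disorders* MedDRA query; both get the same risk differences as AESIs. SAP 7.3 plots individual trajectories for patients with ALT or AST above 3 × ULN, so any 3d case with a central-laboratory value appears there. Protocol 10.6 and 11.3.6.2 ask for repeat tests in any suspected liver injury. Still, the query works only if the event is coded to a hepatic term, so one recorded as nausea or rash could be missed. None of these routes yields the AESI count or the AESI-specific narrative.

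**Fast reporting is hardly lost.** Protocol 14.1 and 16.1 set a similar 2-working-day target for all eCRF data, and serious events go to the sponsor within 24 hours regardless. This stands; what is lost is the dedicated page and its content.

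**No time-to-event analysis is lost.** Protocol 12.4 promises one for each AESI but defers the detail to the SAP. SAP 7.2 plans such plots only for injection site reactions and abdominal pain, and Protocol 12.1 lets the SAP override. This stands, and I do not count it as a loss.

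**The lists need not match.** A stopping rule and a signal definition serve different ends, and the AESI is already wider in one respect because it drops the 2-week duration in 3a. The symptoms in 3d are also non-specific here: nausea, vomiting and fatigue were each reported in more than 20% of Phase 2 patients (Protocol 4.3.2). That would be a possible reason for omitting 3d, but neither document gives it. Where the lists differ in 3a, the AESI is the wider of the two; only for 3d can treatment be stopped with no AESI.

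**A note may be missing.** Criteria 3a to 3d carry asterisks, but no matching note is visible in 7.5 in the text available. If a note there asks for extra data, part of the data request may apply to 3d after all. It would not change the AESI definition or count.

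**Conclusion.** The mismatch is real and limited. A patient with baseline ALT or AST above 1.67 × ULN can be stopped under 7.5(3d) and stay outside the liver AESI count, listing, risk difference and structured narrative. The count *can be* understated. To say that it *is* understated would need the number of patients with such baselines and events, which the documents do not give, so no expected count can be stated.

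The conclusion rests on three assumptions: that the three-part AESI definition is applied as a closed list, that the first AESI criterion means a value above 3 × baseline, and that no unseen note extends the definition. It says nothing on whether any liver threshold is clinically right. The correction is worth making because it is cheap and no other planned output fills the gap.

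**What to change.** Reconcile Protocol 7.5 item 3 with 11.4.1.2. For reporting and analysis only, state in 11.4.1.2 and in SAP 7.2 that any event meeting a liver criterion in either section counts as a suspicion-of-liver-injury AESI. For patients already treated, identify cases from the recorded discontinuation reasons and the central laboratory data, preferably before unblinding, and request the structured liver narrative for any that lack it.

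The cost is about two lines of text and no new data source. The downside is a few more AESI narratives, some triggered by non-specific symptoms. The stopping rule and its thresholds stay as they are.
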